11.3.2 Persistent or Recurrent Adverse Events

A persistent AE is one that extends continuously, without resolution, between patient evaluation time points. Such events should only be recorded once on the SAE Report Form and/or the AE

CONFIDENTIAL

STUDY DRUG: INCB039110 (ITACITINIB)
FINAL PROTOCOL DATE: 26 OCTOBER 2021

INNOVATIONS STUDY NUMBER: BMT 29
VERSION 4

eCRF screen. If a persistent AE becomes more severe or lessens in severity, it should be recorded on a separate SAE Report Form and/or AE eCRF screen.

A recurrent AE is one that occurs and resolves between patient evaluation time points, and subsequently recurs. All recurrent AEs should be recorded on an SAE Report Form and/or AE eCRF screen.

11.3.3 Abnormal Laboratory Values

If an abnormal laboratory value or vital sign is associated with clinical signs and/or symptoms, the sign or symptom should be reported as an AE or SAE, and the associated laboratory value or vital sign should be considered additional information that must be collected on the relevant eCRF screen. If the laboratory abnormality is a sign of a disease or syndrome, only the diagnosis needs to be recorded on the SAE Report Form or AE eCRF screen.

Abnormal laboratory values will be reported as an AE if the laboratory result requires an adjustment in the study drug(s) or discontinuation of treatment and/ or laboratory findings require additional testing or surgical intervention, a laboratory result or finding is associated with accompanying symptoms; or a laboratory result is considered to be an AE by the Investigator.

11.3.4 Deaths

Deaths that occur during the protocol-specified AE reporting period that are attributed solely to progression of disease, as determined by the Investigator, will be recorded on the “End of Study” eCRF screen. All other on-study deaths, regardless of attribution, will be recorded on an SAE Report Form and expeditiously reported to the Innovations Safety Department.

When recording a SAE with an outcome of death, the event or condition that caused or contributed to the fatal outcome should be recorded as the single medical concept on the SAE Report Form and Adverse Event eCRF screen. If the cause of death is unknown and cannot be ascertained at the time of reporting, record “Death NOS” (death, cause unknown) on the eCRF Adverse Event screen. During post-study survival follow-up, deaths attributed to progression of disease will be recorded only on the “Follow-Up Summary” and “Death Page” eCRF screens.

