10.3 Analysis Population

The following analysis populations will be used:

- The Response Evaluable Analysis Set is defined as all patients with cGVHD who received at least one cycle of itacitinib and completed at least one post-baseline disease assessment.
- The Safety Analysis Set is defined as all patients who received at least one dose of itacitinib.

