10.4.2 Efficacy Analysis

All efficacy analyses will be performed using the Response Evaluable Analysis Set.

- ORR is defined as the proportion of patients with a cGVHD status of CR or PR after 6 months of treatment according to the NIH Consensus Criteria (Lee et al. 2015).
- Overall Survival (OS) is defined as the time from the first day of study drug administration (Day 1) to death on study. Patients who are alive will be censored at the date of last known date alive.

For ORR, the estimates and the associated 95% CIs (based on the Clopper-Pearson method) will be calculated.

For OS, a Kaplan-Meier curve will be generated and the median time to event and the associated 95% CIs will be provided.

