10.4.3 Safety Analysis

Safety will be assessed through the analysis of the reported incidence of treatment-emergent AEs. Treatment-emergent AEs are those with an onset on or after the initiation of therapy, and will be graded according to NCI CTCAE Version 5. A copy of CTCAE scoring system may be downloaded from: http://evs.nci.nih.gov/ftp1/CTCAE/CTCAE_5.0_2010-06-14_QuickReference_8.5x11.pdf.

The AEs will be coded using Medical Dictionary for Regulatory Activities (MedDRA) and summarized using system organ class and preferred term for all patients in the Safety Analysis Set. In addition, summaries of SAEs, AEs leading to treatment discontinuation, AEs by maximum NCI CTCAE grade, and AEs related to study treatment will also be presented.

Other safety endpoints including laboratory results, vital signs, ECG findings, and other protocol-specified tests will be listed and/or summarized for all patients in the Safety Analysis Set.

Concomitant medications will be coded using the World Health Organization-Drug Dictionary and they will be listed and summarized.

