11.2 Serious Adverse Event Reporting by Investigators

Adverse events classified by the treating Investigator as serious require expeditious handling and reporting to the Innovations Safety Department in order to comply with regulatory requirements. Determination of life-threatening or serious is based on the opinion of the Investigator.

Serious AEs may occur at any time from the signing of the informed consent form through the 30-day follow-up period after the last dose of study drug. **The Innovations Safety Department must be notified of all SAEs, regardless of causality, within 24 hours of the first knowledge of the event by the treating physician or research personnel.**

To report an SAE, the SAE Report Form should be completed with the necessary information.

The SAE report should be sent to the Innovations Safety Department via fax or e-mail using the following contact information (during both business and non-business hours):

Sarah Cannon Innovations Safety Department

Safety Dept. [contact]

Safety Dept. Email: [contact]

Transmission of the SAE report should be confirmed by the site personnel submitting the report.

Follow-up information for SAEs and information on non-serious AEs that become serious should also be reported to the Innovations Safety Department as soon as it is available; these reports should be submitted using the Innovations SAE Report Form.

Investigators must report SAEs and follow-up information to their responsible IRB according to the policies of the responsible IRB.

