11.3 Recording of Adverse Events and Serious Adverse Events

11.3.1 Diagnosis versus Signs and Symptoms

All AEs should be recorded individually in the patient's own words (verbatim) unless, in the opinion of the Principal Investigator or designated physician, the AEs constitute components of a recognized condition, disease, or syndrome. In the latter case, the condition, disease, or syndrome should be named rather than each individual sign or symptom. If a constellation of signs and/or symptoms cannot be medically characterized as a single diagnosis or syndrome at the time of reporting, each individual event should be recorded as an AE or SAE as appropriate on the relevant form(s) (SAE Report Form and/or AE eCRF screen). If a diagnosis is subsequently established, it should be reported as follow-up information is available. If a diagnosis is determined subsequent to the reporting of the constellation of symptoms, the signs/symptoms should be updated to reflect the diagnosis.

Progression of malignancy (including fatal outcomes), if documented by use of appropriate method (for example, as per RECIST criteria for solid tumors), should not be reported as an SAE.

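### Overall survival is timed from first dose but analysed on a set that patients must survive about one cycle to enter, so Cycle 1 deaths are left out

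*Combined protocol and SAP*

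**What the plan says.** OS is a secondary objective (Section 2.2). Section 10.4.2 lists it under efficacy and states: "All efficacy analyses will be performed using the Response Evaluable Analysis Set". Its clock starts on the first day of study drug and stops at death on study; living patients are censored when last known alive.

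Section 10.3 defines two sets. The Response Evaluable set holds patients with chronic GVHD (cGVHD) who "received at least one cycle of itacitinib and completed at least one post-baseline disease assessment". The Safety Analysis Set needs only one dose. A cycle is 28 days (Section 5.1.1), and the first scheduled response assessment is Cycle 2 Day 1 (Section 6.4), with a window of ±7 days (Appendix D).

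On deaths, Section 11.3.4 makes two routes. The first is for "Deaths that occur during the protocol-specified AE reporting period that are attributed solely to progression of disease", with the investigator as judge; these are recorded on the End of Study eCRF screen. For the rest: "All other on-study deaths, regardless of attribution, will be recorded on an SAE Report Form and expeditiously reported".

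Section 10.4.3 plans treatment-emergent AE tables on the Safety Analysis Set, plus "summaries of SAEs, AEs leading to treatment discontinuation, AEs by maximum NCI CTCAE grade, and AEs related to study treatment will also be presented". It names no summary of deaths. Section 10.4.1 plans a disposition summary that includes withdrawals from treatment or study for any reason.

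**The concern.** A survival analysis that starts at first dose should include everyone who had a first dose. Here entry to the analysis depends on something that happens about four weeks after the clock starts. On the plain reading of the one-cycle rule, no death can occur in the analysed set before about Day 28, so the early part of the Kaplan-Meier curve is flat by construction. Cycle 1 deaths are dropped whatever their cause, and each one dropped pushes the estimate up.

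The usual reassurance about exempting progression deaths from SAE reporting is that OS will pick them up. For a death in Cycle 1 it does not. In an open-label study of an immunosuppressant, an early death may reflect lack of effect or drug harm, and the reader of the report would want to see it as a death.

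The exemption in Section 11.3.4 also does not say which disease it means. The protocol uses progression language both for cGVHD and for the malignancy, so sites could apply it differently.

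**Working it through.** **The plan's own figure.** Section 10.2 gives a 95% interval width of 0.266 for 40 patients at a proportion of 0.200. The Clopper-Pearson interval for 8/40 is 0.0905 to 0.3565, width 0.2660, so the figure reproduces. It concerns response rate and does not bear on OS; the documents give no OS figure.

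**Step 1: who is in OS.** Consider a patient who takes at least one dose and dies before completing 28 days.
- Safety Analysis Set: included (one dose).
- Response Evaluable set: excluded, because a full cycle was not received. The assessment condition will usually fail too, since it is first scheduled on Day 29 (28 + 1), or Day 22 at the earliest within the window. An end-of-treatment assessment in Cycle 1 would meet that condition but not the one-cycle condition.
- OS: excluded, because it follows the Response Evaluable set.

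**Step 2: where each kind of death appears.**

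| Death | In OS | In SAE summary |
|---|---|---|
| Cycle 1, not solely progression | No | Yes |
| Cycle 1, solely progression | No | No |
| Later in an evaluable patient, not solely progression, within AE reporting period | Yes | Yes |
| Later in an evaluable patient, solely progression | Yes | No |

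The OS gap covers the first two rows. Only the second row is missing from both places; it remains in the disposition counts of Section 10.4.1, as a withdrawal.

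**Step 3: size.** The documents give no rate of death before evaluability in cGVHD, so these are assumptions: 40 treated, k Cycle 1 deaths excluded, no other exclusions, no censoring. Then

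S(all treated) = S(evaluable) × (40 − k)/40, and the overstatement is S(evaluable) × k/40.

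With S(evaluable) = 80%:
- k = 1: 0.80 × 39/40 = 78%, overstated by 2 points
- k = 2: 0.80 × 38/40 = 76%, 4 points
- k = 3: 0.80 × 37/40 = 74%, 6 points
- k = 4: 0.80 × 36/40 = 72%, 8 points

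Over k = 1 to 4 the range is 1.75 to 7 points at 70% survival and 2.25 to 9 points at 90%. A whole-patient example: 2 deaths in Cycle 1 and 6 later leave 32 alive. That is 32/40 = 80.0% of those treated but 32/38 = 84.2% of those evaluable.

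**Step 4: chance that it matters at all.** With an assumed early-death probability q, P(at least one among 40) = 1 − (1 − q)^40:
- q = 1%: 33% (0.4 expected)
- q = 2.5%: 64% (1 expected)
- q = 5%: 87% (2 expected)
- q = 10%: 99% (4 expected)

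**Step 5: what the exemption covers.** Section 11.3.1 limits its own exemption to malignancy: "Progression of malignancy (including fatal outcomes), if documented by use of appropriate method". Section 11.3.7 uses disease progression for metastasis. Section 8.3 uses it for cGVHD that needs further systemic therapy. Section 11.3.6 has worsening of a pre-existing condition recorded as an AE or SAE. Section 11.1.2 lists death as a seriousness outcome, and under Section 11.2 the safety department "must be notified of all SAEs, regardless of causality, within 24 hours". Section 11.3.4 does not say how it fits with these.

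**The case against.** A reader might infer that an early progression death would appear in no planned summary. The documents do not support that. The disposition summary counts withdrawals for any reason and is not restricted to evaluable patients, so the patient would be counted there, though nothing says the entry would be shown as a death.

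A reader might also take the exemption to cover any death linked to disease. It covers only deaths attributed solely to progression. Deaths with infection, toxicity or mixed cause go on an SAE form. AEs before the death are still recorded from consent to 30 days after treatment (Section 11.1.5.2), worsening of a pre-existing condition is recordable (Section 11.3.6), and both feed the safety tables.

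A third tempting step is to scale the earlier itacitinib study in acute GVHD, where 9 of 29 patients (31.0%) had fatal treatment-emergent AEs (Section 1.1.2), to this trial. That figure is from a different condition, and those deaths were captured as AEs. It does not forecast uncaptured Cycle 1 deaths here.

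Finally, this is a single-arm pilot with no hypothesis test. A shift of 80.0% to 84.2% is small against the exact 95% interval for 32/40, about 64% to 91%. That is true, but the interval describes chance error. The exclusion of Cycle 1 deaths is systematic, always in the favourable direction, and avoidable.

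On the wording of Section 11.3.4, the neighbouring exemption suggests malignancy was meant. Section 8.3 keeps the other reading open, so this part stands as a request for clarification.

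**Conclusion.** The concern holds for the OS analysis set. As written, the plan leaves Cycle 1 deaths of any cause out of a survival estimate that starts at first dose. Under the stated assumptions this overstates survival by about 2 points per excluded death at 80% survival, or 2 to 8 points for 1 to 4 deaths among 40. If no one dies in Cycle 1, there is no effect from this source. The set also drops patients who stop drug in Cycle 1 and live on or die later; the illustration ignores them, and the documents do not allow their net effect to be judged.

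The further gap, in which a death is missing from both OS and the SAE summary, needs two things together: death before evaluability and attribution solely to progression. Even then the patient remains visible as a withdrawal. This is secondary to the choice of analysis set.

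**What to change.** - **Section 10.4.2:** run OS on the Safety Analysis Set, already defined in Section 10.3 as all patients with at least one dose. Response rate is a separate matter and need not move with it.
- **Section 10.4.3:** add a table of all deaths on the Safety Analysis Set, by cause and by time from last dose, drawing on the End of Study, SAE and survival follow-up records.
- **Section 11.3.4:** state which disease the exemption covers, and reconcile it with Sections 8.3, 11.1.2, 11.2, 11.3.1 and 11.3.6.

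The cost is one extra table and a few sentences. Deaths are already recorded, so the OS change needs no new data collection. Reported OS may be slightly less favourable, and depending on how the exemption is settled there may be a few more SAE reports.

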11.3.5 Hospitalization, Prolonged Hospitalization, or Surgery

Any AE that results in hospitalization of >24 hours or prolongation of pre-existing hospitalization should be documented and reported as an SAE unless specifically instructed otherwise in this protocol. There are some hospitalizations that do not require reporting as an SAE.

Treatment within or admission to the following facilities is not considered to meet the criteria of “inpatient hospitalization” (although if any other SAE criteria are met, the event must still be treated as an SAE and immediately reported):

- Emergency Department or Emergency Room
- Outpatient or same-day surgery units
- Observation or short-stay unit
- Rehabilitation facility

CONFIDENTIAL

STUDY DRUG: INCB039110 (ITACITINIB)
FINAL PROTOCOL DATE: 26 OCTOBER 2021

INNOVATIONS STUDY NUMBER: BMT 29
VERSION 4

- Hospice or skilled nursing facility
- Nursing homes, Custodial care or Respite care facility

Hospitalization during the study for a pre-planned surgical or medical procedure (one which was planned prior to entry in the study), does not require reporting as an SAE to the Innovations Safety Department.

11.3.6 Pre-Existing Medical Conditions

A pre-existing medical condition is one that is present at the start of the study. Such conditions should be recorded on the General Medical History eCRF screen. A pre-existing medical condition should be recorded as an AE or SAE only if the frequency, severity, or character of the condition worsens during the study. When recording such events on an SAE Report Form and/or AE eCRF screen, it is important to convey the concept that the pre-existing condition has changed by including applicable descriptors.

11.3.7 New Cancers

The development of a new primary cancer should be regarded as an AE and will generally meet at least one of the seriousness criteria (see Section 11.1.2). New primary cancers are those that are not the primary reason for the administration of the study treatment and have developed after the inclusion of the patient into the study. They do not include metastases of the original cancer. Symptoms of metastasis or the metastasis itself should not be reported as an AE/SAE, as they are considered to be disease progression.

11.3.8 Pregnancy, Abortion, Birth Defects/Congenital Anomalies

If a patient becomes pregnant while enrolled in the study, a Pregnancy Form should be completed and faxed to the Innovations Safety Department. The Innovations Safety Department should be notified expeditiously, irrespective of whether or not it meets the criteria for expedited reporting. Abortions (spontaneous, accidental, or therapeutic) must also be reported to the Innovations Safety Department.

If a female partner of a male patient becomes pregnant during the male patient's participation in this study, this must be reported to the Innovations Safety Department immediately. Every effort should be made to follow the pregnancy for the final pregnancy outcome.

Congenital anomalies/birth defects always meet SAE criteria, and should therefore be expeditiously reported as an SAE, using the previously described process for SAE reporting. A Pregnancy Form should also have been previously completed, and will need to be updated to reflect the outcome of the pregnancy.

11.3.9 Itacitinib Overdose

Symptomatic and non-symptomatic overdose must be reported in the eCRF. Any accidental or intentional overdose with the study treatment that is symptomatic, even if not fulfilling a seriousness criterion, is to be reported to the Innovations Safety Department no greater than 24 hours from first knowledge of the event using the corresponding screens in the eCRF and following the same process described for SAE reporting (see Section 11.2).

CONFIDENTIAL

STUDY DRUG: INCB039110 (ITACITINIB)
FINAL PROTOCOL DATE: 26 OCTOBER 2021

INNOVATIONS STUDY NUMBER: BMT 29
VERSION 4

There has been no clinical experience with over dosage of itacitinib. The highest total daily dose evaluated in clinical studies was 1200 mg (600 mg twice daily). No unexpected TEAEs were associated with doses of this level. Treatment of a suspected overdose with itacitinib should consist of general supportive measures, as needed.

For information on how to manage an overdose of itacitinib, see the IB.

11.4 Incyte Corporation Serious Adverse Event Reporting Requirements

The Innovations Safety Department will forward SAE information to Incyte's Pharmacovigilance (PhV) Department via email ([contact]) within 1 business day of the Innovations Safety Department personnel becoming aware of the SAE.

If necessary, the Incyte PhV representative or designee will query the Innovations Safety Department (within 48 hours of receipt) for additional information to ensure a valid case prior to distributing the report for internal Incyte review.

Innovations is responsible for reporting relevant SAEs to the competent authority, other applicable regulatory authorities, and participating Investigators, in accordance with International Conference on Harmonisation (ICH) guidelines, and FDA regulations.

Incyte in turn will report relevant events originating from this study to the applicable Incyte IND(s) and will distribute Investigator Notifications to Investigators participating in the applicable Incyte IND(s).

11.4.1 Sponsor Assessment of Unexpected Events

The Sponsor is responsible for assessing an AE or suspected AE as “unexpected”.

An AE or suspected adverse reaction is considered “unexpected” when the following conditions occur:

- Event(s) is not mentioned in the IB (or current US Package Insert [USPI])
- Event(s) is not listed at the specificity or severity that has been observed
- An event(s) is not consistent with the General Investigative Plan or in the current application
- Includes AEs or SAR that may be anticipated from the pharmacological properties of the study drug, or that occur with members of the drug class, but that have previously been observed under investigation.

Known as Suspected Unexpected Serious Adverse Reactions (SUSAR), these events suspected (by the Investigator or Sponsor) to be related to the study drug, are unexpected (not listed in the Investigator's Brochure or USPI), and are serious (as defined by the protocol) and require expedient submission to relevant health authorities within 7 days (fatal or life-threatening events) or 15 days (all serious events), or as defined by law. The term SUSAR is used primarily in the reporting of events to regulatory authorities.

Expected AEs are those events that are listed or characterized in the current IB or current IB.

CONFIDENTIAL

STUDY DRUG: INCB039110 (ITACITINIB)
FINAL PROTOCOL DATE: 26 OCTOBER 2021

INNOVATIONS STUDY NUMBER: BMT 29
VERSION 4

11.4.2 Funding Partner Reporting for Clinical Studies Under an Investigational New Drug Application

All written IND Safety Reports submitted to the FDA by the Innovations Safety Department must also be sent to the pharmaceutical company that is supporting the study with either funding or drug supply:

Incye Corporation
[contact]

12. QUALITY ASSURANCE AND QUALITY CONTROL

12.1 Study Monitoring, Auditing, and Inspecting

The Investigator will permit study-related monitoring, quality audits, and inspections by Incyte Corporation, or its representative(s), government regulatory authorities, and the IRB(s) of all study-related documents (e.g., source documents, regulatory documents, data collection instruments, case report forms). The Investigator will ensure the capability for inspections of applicable study-related facilities. The Investigator will ensure that the study monitor or any other compliance or Quality Assurance reviewer is given access to all study-related documents and study-related facilities.

At the discretion of Innovations, Source Document Verification (SDV) may be performed on all data items or a percentage thereof.

Participation as an Investigator in this study implies the acceptance of potential inspection by government regulatory authorities, the IRB(s), and/or Innovations or its representative(s).

